7.2.5 Sponsor Responsibility for Reporting Adverse Events

All AEs will be reported to regulatory authorities, IRB/IECs and investigators in accordance with all applicable global laws and regulations.

8 STATISTICAL ANALYSIS PLAN

8.1 Statistical Analysis Plan Summary

No inferential statistical analyses will be performed; however, the data will be summarized overall and by treatment dose. Discrete variables will be summarized with counts and percentages; continuous variables will be summarized with means, standard deviations, and ranges.

Data will be summarized for safety by evaluating physical examinations, serum chemistry values, and hematology values. Efficacy will be assessed by changes in PSA and tumor response, based upon CT/MRI scans and evaluations consistent with RECIST, irRECIST criteria and overall survival.

8.2 Statistical Analysis Plan

8.2.1 Analysis Sets

The safety population will include all subjects who have been treated with at least one dose of ADXS31-142 or pembrolizumab (MK-3475).

All subjects who complete at least one cycle of study treatment will be included in the efficacy analyses. Characterization of the Study Population

Distributions of the following baseline data will be described by dose group:

- Demographics
- AJCC TNM prostate cancer stage
- Prior treatments and regimen for prostate cancer
- ECOG Performance Status
- Physical examination parameters

- Vital signs
- Baseline safety labs including hematology and serum chemistry
- Baseline immunology data
- [REDACTED]
- [REDACTED]

8.2.2 *Study Conduct*

Information about study conduct will be presented by treatment dose. Subject disposition at the end of the study will be tabulated including the number of subjects who completed the study as well as the reason for discontinuation for non-completers. The number of subjects in each of the analysis populations, the duration of time on study, and the number of injections will also be displayed. The number and type of protocol violations will be summarized.

8.2.3 *Safety Endpoints*

AEs will be coded using MedDRA and will be presented by System/Organ/Class and preferred term. Some AEs will be categorized and summarized by Grade as defined in CTCAE v 3.0. Concomitant medications will be coded using the CTCAE v 4.0 and summarized by drug class and generic name.

Tables and graphs will show changes from baseline through one year in:

- Physical examination
- Vital signs
- Safety labs, including hematology and serum chemistry

Other safety data that will be presented include:

- DLT
- Adverse events along with their severity and potential relationship to study treatment
- Injection site reactions
- Concomitant medications
- Prophylaxis treatment

8.2.4 ***Efficacy Endpoints***

- Tumor response, time to tumor progression using RECIST, irRECIST or PCWG2 as appropriate
- Survival of subjects at timepoints up to 24 months
- PFS of subjects at timepoints up to 24 months
- [REDACTED]

[REDACTED]

Duration of response will be measured from the time the measurement criteria are met for irCR/irPR (whichever is first recorded) until the first date that progressive disease or death is objectively documented. Subjects who do not relapse will be censored at the day of their last tumor assessment.

Time to progression will be defined as the time from the first day of treatment until the date progressive disease or death is first reported. Subjects who die without a reported prior progression will be considered to have progressed on the day of their death. Subjects who did not progress will be censored at the day of their last tumor assessment.

Tumor response rate is the total number of CRs plus PRs divided by the number of treated subjects. Disease control rate is the number of subjects who have CR+PR+SD for a minimum of 12 weeks following the first day of treatment, divided by the number of response-evaluable subjects.

[REDACTED]

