6.2 Part B Flow Chart – ADXS31-142 Monotherapy + Pembrolizumab (MK-3475) Combination Therapy

Study Procedure	Screening ²	12 Week Treatment Cycle ¹								Follow up		
		Wk 1	Wk 3 ³	Wk 4	Wk 6 ³	Wk 7	Wk 9 ³	Wk 10	Wk 12	End of Therapy procedures	30- & 90-Day Follow-up ⁴	Lm Surveillance Monitoring Period ¹³
	+ 28 days											
Administrative Procedures												
Informed consent ⁵	X											
Inclusion/Exclusion criteria	X											
Demographics/Medical history	X											
Prior/Concomitant medication	X	X	X	X	X	X	X	X	X	X	X	X
Pembrolizumab (MK-3475) Administration ⁶		X		X		X		X				
NSAIDs & Antiemetic Administration ⁷		X		X		X						
ADXS31-142 Administration ⁸		X		X		X						
Dispense/Prescribe oral prophylactic antibiotics ⁹		X		X		X				X		
Clinical Procedures/Assessments												
Review Adverse events ¹⁰		X	X	X	X	X	X	X	X	X	X	X
Physical examination	X	X		X		X		X		X		
Vital signs ¹¹	X	X		X		X		X		X		
ECOG performance status	X	X		X		X		X		X		
Laboratory Procedures/Assessments: analysis performed by LOCAL laboratory												
CBC with Differential	X	X		X		X		X		X		X
Serum Chemistry Panel	X	X		X		X		X		X		X
PT/INR and aPTT	X											
Urinalysis	X	X		X		X		X		X		
TSH, T3, T4 ¹²		X		X		X		X				

CMP (including CRP, ESR) and Blood Cultures												X
Efficacy Measurements/Correlative Studies												
Tumor Imaging ¹⁴	X							X	X			X

1. Repeating 12-week treatment cycles
2. Baseline tumor evaluation will be performed 28 days prior to first dose.
3. Week 3, Week 6 and Week 9 visits will be performed during Cycle 1 only. After Cycle 1, these visits are not required.
4. Safety follow-up will be conducted via a telephone call 30 days (\pm 5 days) and 90 days for SAE assessment after the last study treatment to confirm the resolution of any ongoing AEs. In addition, [REDACTED] testing every 4 weeks and imaging every 12 weeks (\pm 1 week) should continue for subjects who discontinue treatment for reasons other than progression (Refer to Section 7.1.5.3. Post-Treatment Visits).
5. Prior to conducting screening evaluations. Signing of informed consent does not start the 28 days screening window.
6. Prior to administering any prophylactic medications, place a [REDACTED] Pembrolizumab (MK-3475) is to be administered before ADXS31-142 through a temporary IV with a [REDACTED] wait period between infusions.
7. Subjects will receive premedications at least 30 minutes before each ADXS31-142 infusion.

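### The efficacy set requires completion of a 12-week cycle while time to progression runs from first dose, so time to progression, PFS and survival are biased upward, and possibly disease control rate too

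*Combined protocol and SAP*

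**What the plan says.** Section 8.2.1 of the combined protocol and SAP defines two sets. The safety population needs one dose of either drug. For efficacy: "All subjects who complete at least one cycle of study treatment will be included in the efficacy analyses".

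The flow charts fix the cycle length ("Repeating 12-week treatment cycles"). What counts as completing a cycle is not stated. ADXS31-142 is given in Weeks 1, 4 and 7, and Part B pembrolizumab also in Week 10.

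Section 8.2.4 then treats each endpoint differently:

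- Time to progression is "the time from the first day of treatment until the date progressive disease or death is first reported". A death without earlier progression counts as an event.
- PFS appears only as "PFS of subjects at timepoints up to 24 months", and survival is listed in the same way. The visible text gives neither its own time origin nor a denominator.
- Response rate: "Tumor response rate is the total number of CRs plus PRs divided by the number of treated subjects".
- Disease control rate counts CR, PR or SD lasting at least 12 weeks from first treatment, "divided by the number of response-evaluable subjects". The visible text does not define that group.
- Duration of response runs from the first irCR or irPR, so it concerns responders only.

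Section 5.10 rules out replacement. Section 3.2 says the anti-tumor and PFS signal is meant to inform a later randomized Phase 2 trial. Section 8.1 says the analysis is descriptive.

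**The concern.** Membership of the efficacy set depends on what happens after the clock starts. Someone in the set cannot, by definition, have died before completing cycle 1, yet the time spent completing it is credited to the time-to-event endpoints. This is immortal-time selection.

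The protocol gives several routes out of cycle 1 that go with a poor outcome: death, clinical progression, unacceptable toxicity and intercurrent illness (Sections 2.1.2 and 5.9), and a DLT at Dose Level -1, which ends study treatment (Section 5.2.1.1.1). The DLT window itself closes one week after the second ADXS31-142 dose, inside cycle 1.

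With about 30 subjects planned at the Part B RP2D, a few such losses move the estimates visibly. At stake are the planning assumptions for the randomized trial named in Section 3.2. A PFS curve without its early failures would make the regimen look better than it is.

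**Working it through.** The plan states no median PFS, response rate or early-dropout rate, so there is no figure of its own to reproduce. The direction of the bias follows from the definitions. The size below is an illustration.

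**Assumptions.** PFS is exponential with median m months, so S(t) = exp(−ln 2 × t / m). A month is 30.4375 days. Medians of 3 to 12 months are assumed.

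**Inputs from the documents.** The cycle is 12 weeks = 84 days = 2.76 months (Section 6). The Week 7 dose falls 42 days (1.38 months) after first dose, and the Week 10 dose 63 days (2.07 months) after.

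**Case 1: every subject with an event before Week 12 is excluded (upper bound).** The share removed is 1 − S(2.76). Reported 6-month PFS is S(6)/S(2.76). The exponential has no memory, so the reported median is m + 2.76.

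| True median (months) | Removed | True 6-month PFS | Reported 6-month PFS | Reported median |
|---|---|---|---|---|
| 3 | 47% | 25% | 47% | 5.8 |
| 4 | 38% | 35% | 57% | 6.8 |
| 6 | 27% | 50% | 69% | 8.8 |
| 9 | 19% | 63% | 78% | 11.8 |
| 12 | 15% | 71% | 83% | 14.8 |

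For m = 4: S(2.76) = 0.620, S(6) = 0.354, and 0.354/0.620 = 0.570. Here 12-week PFS is 100% by construction, against a true 62%. A simulation of one million times at m = 6 agreed (median 8.77, 6-month PFS 68.8%).

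**Case 2: completing a cycle means reaching its last dose (m = 4).**

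- Week 7: S(1.38) = 0.787, so 21% are removed. 6-month PFS is 0.354/0.787 = 45%, and the median rises by 1.4 months.
- Week 10: S(2.07) = 0.699, so 30% are removed. 6-month PFS is 0.354/0.699 = 51%, and the median rises by 2.1 months.

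**Case 3: only a share q of subjects with an event by Week 12 is excluded (m = 6).** The share excluded is e = q × 0.273. Reported 6-month PFS is 0.500/(1 − e). The reported median solves S(t) = 0.5 × (1 − e).

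- q = 25%: e = 0.068, 6-month PFS 54%, median 6.6 months.
- q = 50%: e = 0.136, 6-month PFS 58%, median 7.3 months.
- Truth: 50% and 6.0 months.

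**Denominators (illustrative counts).** Suppose 12 of 30 treated subjects have disease control: 12/30 = 40%. If 20% of the 30 do not complete a cycle and completers are the denominator, it becomes 12/24 = 50%. Suppose 3 of 30 respond: 3/30 = 10.0% as Section 8.2.4 is written. It becomes 3/24 = 12.5% only if Section 8.2.1 overrides that formula.

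**The case against.** Several points on the other side are sound and limit the finding.

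- **Not every efficacy estimate is inflated.** A reader might infer that all are, including a response rate raised by 1/0.62 = 1.6-fold. The documents do not support this. Section 8.2.4 divides responses by treated subjects, and nothing says Section 8.2.1 overrides that. Duration of response is measured within responders and does not gain the extra weeks.
- **Not every first-scan progressor is lost.** The first scan is at Week 10 (±1 week). Under Section 7.1.2.6.4, irPD found at or before the 12-week assessment without rapid clinical deterioration needs a second scan at least 4 weeks later, with treatment continuing meanwhile. That puts confirmation at Week 13 or later, after cycle 1 has ended. Section 7.1.2.6.9 also permits treatment past initial progression. Many of these subjects can complete the cycle. Neither rule keeps in the set those who die, deteriorate rapidly or stop for toxicity.
- **Twelve guaranteed weeks is one reading.** Completion could mean the Week 7 or Week 10 dose, which reduces the bias as case 2 shows but does not remove it.
- **PFS and survival have no stated origin in the visible text, and parts of Section 8.2.4 are redacted.** The first-dose origin comes from time to progression, the only progression-or-death definition given, which is PFS in substance.
- **A response-evaluable denominator is not wrong in itself.** Entry is allowed on PSA or bone progression alone (Section 5.1.2), and bone lesions are non-measurable (Section 7.1.2.6.1). A restriction fixed at baseline could be legitimate, so outright deletion of the term is not established as necessary.
- **The analysis is descriptive and efficacy is secondary.** No error rate or go/no-go rule is affected, and Section 8.2.2 will show the number in each set and the reasons for stopping. That makes the exclusions visible but does not correct the estimates, which are meant to guide another trial.

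**Conclusion.** The concern holds for time to progression, PFS and survival. It holds for disease control rate if response-evaluable means cycle completers. For response rate the problem is a conflict between Sections 8.2.1 and 8.2.4, not a demonstrated bias.

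The upward direction needs no assumed median: it follows from dropping early deaths and rapid progressors while timing from first dose. Toxicity stops add to it to the extent that those subjects later do worse than the rest.

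The size cannot be derived from the documents. It would be tempting to quote 38% removed and 2.8 months added to the median as the estimate. Those figures assume a 4-month exponential median and exclusion of every event before Week 12, which the irPD confirmation rule makes unlikely. They are an upper bound for that median. Under the milder assumptions of case 3, the excess is 4 to 8 percentage points in 6-month PFS and 0.6 to 1.3 months in the median.

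**What to change.** Amend Sections 8.2.1 and 8.2.4 as follows:

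- Define the efficacy set as all subjects who received at least one dose of study treatment. Use it for response rate, time to progression, PFS and survival.
- State that PFS and survival are timed from first dose.
- Count treated subjects with no post-baseline assessment as non-responders.
- Report disease control rate over all treated subjects, or over a subset defined only by baseline characteristics (for example, evaluable disease at baseline), never by cycle completion.
- Keep cycle-1 completers only as a labelled sensitivity analysis, and say what completing a cycle means.

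The cost is SAP wording and less favourable reported figures. No extra subjects, visits or data are needed.

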7.1.2.6.4 Immune-Related Response in Measurable Lesions (irRECIST)

In addition to evaluation using RECIST 1.1 criteria, an immune response adaptation of RECIST will be applied to this trial. The essential differences between irRECIST and RECIST criteria are as follows:

- New measurable lesions do not necessarily constitute progressive disease and they should be added into the total tumor burden. New non-measurable lesions do not constitute disease progression but will prevent the determination of an irCR.
- Subjects with an initial finding of progressive disease (irPD) before or at the 12-week imaging assessment, but without rapid clinical deterioration, require confirmation of irPD with a second, consecutive scan obtained ≥ 4 weeks from the

initiation documentation. Subjects will continue to receive study treatment until irPD is confirmed at this later time point.

At baseline, the sum of the longest diameters (SumD) of all target lesions (up to 2 per organ and 5 in total) is measured. At each subsequent tumor assessment, the SumD of the target lesions and of new, measurable lesions (≥ 10 mm [lymph nodes ≥ 15 mm in shortest diameter]; up to 2 new lesions per organ, total 5 new lesions) are added together to provide the total measurable tumor burden (TMTB):

$$\text{TMTB} = \text{SumD target lesions} + \text{SumD new, measurable lesions}$$

Percentage changes in TMTB per assessment timepoint describe the size and growth kinetics of both old and new measurable lesions as they appear. At each tumor assessment, the response in target and new measurable lesions is defined based on the change in TMTB (after ruling out irPD) as follows:

- Complete Response (irCR): complete disappearance of all target and new, measurable lesions, with the exceptions of lymph nodes which must decrease to <10 mm in short axis
- Partial Response (irPR): decrease in TMTB $\geq 30\%$ relative to baseline (see below)
- Stable Disease (irSD): not meeting criteria for irCR or irPR, in absence of irPD
- Progressive Disease (irPD): increase in TMTB $\geq 20\%$ relative to nadir

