7.1.2.6.8 Best Overall Response (RECIST 1.1)

The best overall response is the best response recorded from the start of the study treatment until the end of treatment taking into account any requirement for confirmation. The subject's best overall response assignment will depend on the findings of both target and non-target disease and will also take into consideration the appearance of new lesions [Table 13](#).

Table 13 Best Overall Response (RECIST 1.1)

Target Lesions		Non-Target Lesions		Overall Response
Baseline (Index) and New Measurable Lesions		Baseline Lesions	Unequivocal New Lesions	
CR	CR	CR	No	CR

Target Lesions		Non-Target Lesions		
Baseline (Index) and New Measurable Lesions		Baseline Lesions	Uequivocal New Lesions	Overall Response
CR	Non-CR/Non-PD		No	PR
CR	NE		No	PR
PR	Non-PD or NE		No	PR
SD	Non-PD or NE		No	SD
Not all evaluated	Non-PD		No	NE
PD	Any		Yes or No	PD
Any	PD		Yes or No	PD
Any	Any		Yes	PD

The immune-related best overall response (irBOR) is the best irCR overall response over the study as a whole, recorded between the date of first dose until the last TA prior to subsequent therapy (including tumor resection surgery) for the individual subject in the study (Table 14). As with the primary definitions of tumor response, early progression (i.e., irPD occurring prior to Week 12) will not preclude an irBOR of irCR, irPR or irSD resulting from the Week 12 assessment. An assessment of irPD at or after Week 12 will preclude a subsequent irBOR of irCR, irPR or irSD. However, any post-progression clinical activity in subjects with irBOR of irPD may be summarized for exploratory purposes.

Table 14 Immune-Related Best Overall Response (irBOR)

Target Lesions Baseline (Index) and New Measurable Lesions		Non-Target Lesions ^a		
Total Measurable Tumor Burden (TMTB)		Baseline Lesions	Uequivocal New Lesions	irRC Overall Response
irCR	irCR		No	irCR
irCR	irSD		No	irPR
irPR	irCR or irSD		No	irPR
irSD	irCR or irSD		No	irSD
irPD	Any		Yes or No	irPD
Any	Uequivocal Progression		Yes or No	irPD

Target Lesions Baseline (Index) and New Measurable Lesions		Non-Target Lesions ^a	
Total Measurable Tumor Burden (TMTB)		Baseline Lesions	Uequivocal New Lesions
Any	Any	Yes	irPD

irCR = immune-related complete response; irPR = immune-related partial response; irSD = immune-related stable disease; irPD = immune-related progressive disease

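### Under irRECIST, the single first-reported progression date in section 8.2.4 does not exempt an early irPD that the required repeat scan fails to confirm, so a responder can be given a 9-week time to progression and a negative duration of response

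*Combined protocol and SAP*

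**What the plan says.** Section 8.2.4 (Efficacy Endpoints) lists the progression endpoint as "Tumor response, time to tumor progression using RECIST, irRECIST or PCWG2 as appropriate". It then gives a single event date: time to progression is counted from the start of treatment "until the date progressive disease or death is first reported". Death without earlier progression counts as progression on the day of death, and subjects who do not progress are censored at their last tumor assessment. Duration of response, in the same section, runs from the first irCR or irPR to the earliest objective documentation of progression or death. Neither definition mentions confirmation.

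The response sections treat an early irPD differently. Under section 7.1.2.6.4, subjects with irPD before or at the 12-week imaging, and without rapid clinical deterioration, "require confirmation of irPD with a second, consecutive scan obtained ≥ 4 weeks" after the initial irPD scan. Meanwhile, "Subjects will continue to receive study treatment until irPD is confirmed at this later time point". The footnote to Table 12 (section 7.1.2.6.7) repeats this and says that best overall response includes responses seen after early progression. Section 7.1.2.6.8 says that "early progression (i.e., irPD occurring prior to Week 12) will not preclude an irBOR of irCR, irPR or irSD resulting from the Week 12 assessment".

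The first on-treatment scan is at Week 10, plus or minus 1 week, and later scans are every 12 weeks (section 7.1.5.2).

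**The concern.** Best response under irRECIST looks past an early irPD that reverses. The wording that dates progression does not. The first scheduled scan falls inside the period in which irPD needs confirmation, so the situation arises on the planned schedule. A subject treated through an unconfirmed irPD can also complete a cycle and so enter the efficacy analyses (section 8.2.1).

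The same subject can then appear as a responder in one table and as an early progressor in another. The irRECIST time to progression would become an unconfirmed-progression endpoint and lose the feature that separates it from RECIST 1.1. Section 3.2 gives anti-tumor activity and a PFS signal as a secondary objective, meant to inform the design of a later randomized trial, so these descriptive figures will be used.

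**Working it through.** The plan states no figure for time to progression, number of events or reversal rate, so there is nothing to reproduce. The check has four steps.

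**1. Timing.** Elapsed time at Week w Day 1 is (w − 1) × 7 days from Week 1 Day 1.

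- Week 10: 9 × 7 = 63 days = 9.0 weeks, or 8 to 10 weeks with the 1-week window. The Part B flow-chart footnote speaks of 10 weeks; read as elapsed time, that gives 9 to 11 weeks.
- Earliest repeat scan after a Week 10 irPD: 63 + 28 = 91 days = 13.0 weeks, which is Week 14.

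**2. One subject under each rule.** Take irPD at Week 10 and irPR on the repeat scan at Week 14.

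- Best response: irPR, because the Table 12 footnote counts responses after early progression.
- Time to progression, 8.2.4 read literally: 9 weeks.
- Time to progression with confirmation required: no event at 9 weeks. The subject stays at risk through at least week 13, until a later irPD, death or censoring.
- Duration of response, read literally: starts at week 13, and the first documented progression is at week 9, so 9 − 13 = −4 weeks.

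The response need not come on the repeat scan. A constructed record of total measurable tumor burden:

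| Day | TMTB (mm) | Reading |
|---|---|---|
| Baseline | 50 | – |
| 64 | 61 | 61/50 = +22%, irPD |
| 95 | 48 | 48/50 = −4%, not confirmed |
| 148 | 34 | 34/50 = −32%, irPR |
| 232 | 45 | 45/34 = +32% from nadir, irPD |

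The literal event date is day 64. With confirmation required it is day 232, a difference of 232 − 64 = 168 days for this one subject.

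**3. Cohort scale.** Section 5.2.1.1.3 plans about 30 subjects at the RP2D. Each reverser moves the crude progression-free proportion at 12 weeks by 1/30 = 3.3 points; two move it by 2/30 = 6.7 and three by 3/30 = 10.0. The number of reversers is an assumption.

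**4. Measurement noise alone.** The irPD definition in section 7.1.2.6.4 has no minimum increase in millimetres, whereas section 7.1.2.6.3 requires 5 mm for RECIST 1.1. I simulated 400,000 subjects per setting with no true change. Assumptions, none from the documents: every target lesion 16 mm, independent measurement error with SD 1, 1.5 or 2 mm, and values rounded to 1 mm. irPD is a sum of at least 1.2 times baseline; unconfirmed means that an independent repeat falls below that threshold. Ranges run over the error SDs.

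| Target lesions | irPD at first scan (%) | Share unconfirmed (%) | Unconfirmed irPD (points) |
|---|---|---|---|
| 1 | 3.9 to 17.1 | 53 to 75 | 2.9 to 9.1 |
| 2 | 0.4 to 8.0 | 65 to 90 | 0.3 to 5.3 |
| 3 | 0.04 to 4.1 | 72 to 97 | 0.04 to 2.9 |
| 5 | 0 to 1.2 | 80 to 100 | 0 to 1.0 |

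These rates apply only to subjects with measurable disease. Section 5.1.2 allows entry on PSA or bone progression alone, and section 7.1.2.6.1 classes bone lesions as non-measurable. The whole-cohort effect of noise is therefore smaller.

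**The case against.** The strongest reply is that 8.2.4 does not say that an unconfirmed irPD counts. The endpoint line refers to irRECIST as appropriate, so the meaning of progressive disease could be taken from section 7.1.2.6.4, where early irPD needs confirmation. An analyst could reach the later date without any change to the plan. This stands in part. A reader might infer that the SAP deliberately counts progression whether or not it is confirmed; the documents do not support that, because the result comes from the phrase on first reporting together with silence on confirmation. But a second analyst could follow that phrase literally, and the two would report different dates for the same subject. Importing confirmation also leaves open whether a confirmed irPD is dated at the first or the second scan.

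Parts of 8.2.4 are redacted, so a further rule there cannot be excluded. The visible definition is nevertheless complete in itself. Section 7.1.2.6.9 also calls for a repeat scan, but it uses the result to decide on treatment, not to date the event.

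The analyses are descriptive only (section 8.1), and no error rate, threshold or sample size depends on this point. That stands, and it limits the weight.

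**Conclusion.** The point holds as a conflict between the dating rule in 8.2.4 and the plan's own irRECIST rules. It affects irRECIST time to progression and duration of response. First-PD dating fits RECIST 1.1 as the protocol defines it, and nothing here shows a problem for PCWG2.

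It is tempting to conclude that the PFS signal is biased downward. The documents do not support that: PFS has no visible definition of its own, and it is affected only if its irRECIST version uses the same dating.

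The certain part of the size is arithmetic: 9 weeks and minus 4 weeks for the subject described, and 3.3 points per reverser among about 30. How many reversers to expect is unknown. On the assumed lesion size and error SDs, noise alone gives about 3 to 9 points with one target lesion, 0.3 to 5 with two, and at most about 3 with three or more, in subjects with measurable disease only. True pseudo-progression would add to this by an amount the documents do not give. The correction is worth making before analysis because it is cheap and removes an internal contradiction.

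**What to change.** In section 8.2.4, for irRECIST time to progression and duration of response, state that:

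- an early irPD not confirmed by the protocol's repeat scan is not an event, and the subject stays at risk;
- a confirmed irPD is dated at the first irPD scan;
- an irPD with no repeat scan has a named rule, for example an event at the first irPD date, with a sensitivity analysis;
- duration of response ends only at an irPD (or death) after the response began.

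Keep first PD for RECIST 1.1, report the two sets of results separately, and say which dating PFS uses.

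The cost is SAP text and slightly more programming. The repeat scans are already in the protocol, so no new data are needed. The rule for a missing repeat scan is a choice that the documents do not settle, which is why it should be fixed in advance and tested by the sensitivity analysis.
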